3.1.3 Prior and concurrent therapy

- 3.1.3.1 Patients may have had prior systemic therapy without constraint on the number of prior treatment regimens except:
- a) Patients may not have had $>450 \text{ mg/m}^2$ doxorubicin
 - b) Patients may not have had $>3000 \text{ cGy}$ to fields encompassing the entire pelvis
- 3.1.3.2 Patients must not be on any other systemic therapy within the following intervals before study enrollment:
- a) 1 week after stereotactic radiosurgery of the brain or comparable technology
 - b) 4 weeks after cytotoxic chemotherapy or external beam radiation therapy
 - c) 6 weeks after chemotherapy regimens including BCNU (carmustine) or mitomycin C
 - d) patients who experience melanoma progression (by RECIST 1.1 criteria) while on or after treatment with PD-1 or PDL-1 antibody may enroll on this study.

NOTE: Patients must be off PD-1/PDL-1 antibody for at least 2 weeks to assess for delayed toxicity before being enrolled and receiving INCB024360. Patients who are enrolled 2 weeks and up to 6 weeks after the last dose of PD-1/PDL-1 antibody will enroll in cohort B and receive 100mg BID of INCB024360.

Patients enrolled beyond the 6 week period after failing anti-PD-1/PDL-1 will be enrolled in cohort A. Cohort A patients will receive 300mg BID of INCB024360.

Patients must not have active grade 2 autoimmune toxicities attributed to these antibodies at study entry.

- e) 8 weeks after ipilimumab, other CTLA-4 antibody or other immunologically active antibody.

NOTE: Patients receiving prior CTLA-4, anti-PD1 antibody or other immunologic therapy must show evidence of normal pituitary function at baseline and must not have active grade 2 autoimmune toxicities attributed to these antibodies at study entry.

3.1.4 Age ≥ 18 years

[**NOTE:** Because insufficient dosing AE data are currently available on the use of INCB024360 in combination with MELITAC 12.1 in patients <18 years of age, children are excluded from this study, but will be eligible for future pediatric trials.]

3.1.5 ECOG performance status 0–1 (Karnofsky $\geq 70\%$, see [Appendix A](#)).

3.1.6 Life expectancy of at least 6 months

3.1.7 Patients must have normal organ and marrow function as defined below:

- leukocytes	$\geq 3,000/\text{mcL}$
- absolute neutrophil count	$\geq 1,500/\text{mcL}$
- platelets	$\geq 75,000/\text{mcL}$
- hemoglobin	$>9\text{g/dL}$
- total bilirubin	$<1.5 \times \text{institutional upper limit of normal}$ [bilirubin $<3 \times \text{institutional upper limit of normal}$ for Gilbert's syndrome]
- AST(SGOT)/ALT(SGPT)	Up to 2.5 times ULN
- creatinine	$<1.5 \times \text{institutional upper limit of normal}$ OR
- creatinine clearance	$\geq 60 \text{ mL/min}/1.73 \text{ m}^2$ for patients with creatinine levels above institutional normal.
- PT, INR	$\leq 1.5 \times \text{institutional ULN}$ unless patient is therapeutically anticoagulated. If on anticoagulants, PT/INR need to be within appropriate anticoagulation limits for the clinical indication. Patients who are receiving anticoagulants may participate in the trial if their anticoagulation can be stopped safely for several days at the time of each biopsy.
- TSH,	Up to 4 times ULN if T4 is normal
- T4	Within normal limits. If abnormal and patient is receiving thyroid replacement therapy, the thyroid medication may be adjusted and the T4 may be re-tested.

3.1.8 Patients must express HLA-A1+, -A2+, or -A3+ (80% of patients)

3.1.9 LDH $<5 \times$ upper limits of normal

[NOTE: These criteria will select against patients with bulky disease and will select for patients with less disease and earlier disease.]

3.1.10 Participants must not have had prior autoimmune disorders requiring cytotoxic or immunosuppressive therapy, or autoimmune disorders with visceral involvement. Participants must not have an active or inactive autoimmune disorders (e.g., rheumatoid arthritis, moderate or severe psoriasis, multiple sclerosis, inflammatory bowel disease, etc.) Participants who are receiving therapy for an autoimmune or inflammatory disease requiring these therapies are also excluded.

3.1.11 The following will not be exclusionary:

- Resolved ipilimumab associated inflammatory disease
- The presence of laboratory evidence of autoimmune disease (e.g., positive antinuclear antibody [ANA] titer) without associated symptoms
- Subjects with vitiligo, thyroiditis, or atopic dermatitis, but otherwise not meeting this criterion may be enrolled. Individual cases can be discussed with the sponsor.

3.1.12 Not likely curable with surgery alone

3.1.13 Not currently receiving therapy

3.1.14 Females of childbearing potential must have a negative pregnancy test within 48 hours before initiating protocol therapy.

NOTE: The effects of INCIB024360 and MELITAC 12.1 on the developing human fetus are unknown. For this reason, women of child-bearing potential and men must agree to use adequate contraception (hormonal or barrier method of birth control or abstinence) before study entry and for the duration of study participation. Should a woman become pregnant or suspect she is pregnant while she or her partner is participating in this study, she should inform her treating physician immediately. Men treated or enrolled on this protocol must also agree to use adequate contraception before the study, for the duration of study participation, and 4 months after completing INCIB024360 and MELITAC 12.1 administration.

NOTE: Subjects are considered not of child bearing potential if they are surgically sterile, have undergone a hysterectomy, bilateral tubal ligation, or bilateral oophorectomy, or are postmenopausal. Menopause is the age associated with complete cessation of menstrual cycles and menses, and implies the loss of reproductive potential. By a practical definition, the term assumes menopause after 1 year without menses with an appropriate clinical profile at the appropriate age.

3.1.15 Ability to understand and willingness to sign a written informed consent document

3.2 Exclusion Criteria

3.2.1 Patients who have had cytotoxic chemotherapy, radiotherapy, IFN, immunosuppressive therapy, or steroids within 4 weeks (6 weeks for nitrosoureas or mitomycin C) before entering the study or those who have not recovered from AEs due to agents administered more than 4 weeks earlier

3.2.2 Ipilimumab, or other immunologically active therapy within 8 weeks of enrollment.

NOTE: Patients who experience melanoma progression (by RECIST 1.1 criteria) while on or after treatment with PD-1 or PDL-1 antibody may enroll on this study (per section 3.1.3.2 above)

3.2.3 Active immunosuppressive therapy, including concurrent systemic immunosuppressive therapy or steroid therapy with more than 7 consecutive days of steroids within the prior 4 weeks

- The use of prednisone or equivalent <0.125 mg/kg/day (absolute maximum of 10 mg/day) as replacement therapy is permitted.
- Inhaled corticosteroids are permitted.

- 3.2.4 Cardiovascular disease that meets one of the following: congestive heart failure (New York Heart Association Class III or IV), active angina pectoris, or recent myocardial infarction or acute coronary syndrome (within the last 6 months)
- 3.2.5 History of peripheral vascular disease (PWD) that has required surgical or percutaneous intervention or documented PWD that requires medical management with medications such as ASA + Clopidogrel. Patients with Diabetes that is not well controlled are excluded from participation. Not well controlled is defined as a Hgb A1C of greater than 7.5%.
- 3.2.6 Current or history of systemic autoimmune disease requiring systemic therapy, including significant autoimmunity associated with prior ipilimumab therapy or therapy with antibodies to PD-1 or PD-L1
- 3.2.7 Cirrhosis, chronic hepatitis C virus positivity, or chronic hepatitis B infection. Subjects who may not tolerate immune-mediated hepatitis due to compromised hepatic reserve are also excluded from participation including: 1) Subjects with extensive liver metastasis (as judged by the investigator) 2) Subjects who drink more than two standard alcoholic beverages per day on a regular basis 3) Subjects who consume more than 2 grams of Acetaminophen per day on a regular basis.
 - A positive hepatitis B serology indicative of previous immunization (i.e., HBsAb-positive and HBcAb-negative), or a fully resolved acute hepatitis B infection is not an exclusion criterion.
- 3.2.8 Patients who are receiving any other investigational agents for melanoma
- 3.2.9 Patients who have had a grade one or grade two gastrointestinal adverse event during or after receiving anti-CTLA-4, anti-PD1 or anti-PD, without a colonoscopy verifying complete resolution of the adverse event.
- 3.2.10 Patients who have experienced bowel perforation, neurologic involvement, Guillain Barré syndrome, Myasthenia Gravis, Steven Johnson syndrome and other intractable events or grade 4 non-laboratory toxicity.
- 3.2.11 Uncontrolled intercurrent illness including, but not limited to, ongoing or active infection, symptomatic congestive heart failure, unstable angina pectoris, cardiac arrhythmia, or psychiatric illness/social situations that would limit compliance with study requirements
- 3.2.12 Pregnancy, nursing, or unwilling to take adequate birth control during therapy

NOTE: Pregnant women are excluded from this study because INCB024360 and MELITAC 12.1 have the potential for teratogenic or abortifacient effects. Because of unknown but potential risks for AEs in nursing infants secondary to treatment of the mother with INCB024360 and MELITAC 12.1, breastfeeding should be discontinued if the mother is treated with INCB024360 and MELITAC 12.1. These potential risks may

also apply to other agents used in this study.

3.2.13 Known HIV or other history of immunodeficiency disorder

NOTE: HIV-positive patients taking combination antiretroviral therapy are ineligible because of the potential for pharmacokinetic interactions with INCB024360 and MELITAC 12.1. In addition, these patients are at increased risk of lethal infections when treated with marrow-suppressive therapy. Appropriate studies will be undertaken in patients receiving combination antiretroviral therapy when indicated.

3.2.14 Extensive active brain disease, including symptomatic brain metastases or the presence of leptomeningeal disease

- Patients with brain metastasis, after definitive therapy with surgery or stereotactic radiation and stable off steroids for >4 weeks, are eligible.

3.2.15 Any malignancy that has not been in complete remission for at least 3 years

NOTE: Patients with cured basal or squamous cell skin cancer are not excluded. Patients with a history of excised in situ cancers, including breast, cervical, colon, superficial bladder, prostate or other body system are not excluded. Study entry will be allowed at the discretion of the Principal Investigator.

NOTE: Recurrence of the in situ cancer or tumor at the time of study entry would be exclusionary.

3.2.16 Monoamine oxidase (MAO) inhibitor use within the past 3 weeks or prior evidence of serotonin syndrome

3.2.17 History of allergic reactions attributed to compounds of similar chemical or biologic composition to INCB024360, MELITAC 12.1, or other vaccine components

3.2.18 Prior organ allograft or allogeneic transplantation, if the transplanted tissue is still in place

3.2.19 Medical or psychiatric illness that would, in the opinion of the investigator, preclude participation in the study or the ability of patients to provide informed consent for themselves

3.2.20 History of pulmonary disease such as emphysema or chronic obstructive pulmonary disease (COPD), (FEV1>60% of predicted for height and age). Pulmonary function tests (PFTs) are required in patients with prolonged smoking history or symptoms of respiratory dysfunction.

- 3.2.21 Use of any UGT1A9 inhibitor including: acitretin, amitriptyline, androsterone, cyclosporine, dasatinib, diclofenac, diflunisal, efavirenz, erlotinib, estradiol (17-beta), flutamide, gefitinib, gemfibrozil, glycyrhetic acid, glycyrhizin, imatinib, imipramine, ketoconazole, lineoleic acid, mefenamic acid, mycophenolic acid, niflumic acid, nilotinib, phenobarbital, phenylbutazone, phenytoin, probenecid, propofol, quinidine, ritonavir, Sorafenib, sulfapyrazone, valproic acid and verapamil from screening through follow-up period.
- 3.2.22 Low-dose Coumadin (1 mg) is acceptable; however, doses that increase INR are not permitted. If an alternative to Coumadin-based anticoagulants cannot be used, the INR should be monitored weekly after initiation of therapy and upon discontinuation of INCB024360, until INR normalization.

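### Exclusion 3.2.20 attaches FEV1 above 60% of predicted to a history of pulmonary disease without saying whether the figure excludes or permits entry; read literally, such patients with better FEV1 are excluded and those with worse are not excluded by this item

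*Combined protocol and SAP*

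**What the plan says.** Protocol section 3.2 is headed "3.2 Exclusion Criteria", so meeting one of its items makes a patient ineligible. Item 3.2.20 begins: "History of pulmonary disease such as emphysema or chronic obstructive pulmonary disease (COPD), (FEV1>60% of predicted for height and age". The qualifier inside the bracket is "FEV1>60% of predicted for height and age"; the bracket then closes and the sentence ends. The item has one further sentence: "Pulmonary function tests (PFTs) are required in patients with prolonged smoking history or symptoms of respiratory dysfunction". It does not say which test result excludes a patient.

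No other section gives an FEV1 limit or a direction for one. The study calendar in section 10 does not list pulmonary function tests.

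**The concern.** A numeric bound inside an exclusion item is normally read as the range that excludes. On that reading, among patients with a history of lung disease, the item turns away those with better FEV1 and lets those with worse FEV1 pass. That is hard to square with a safety screen. A site that finds this implausible must supply its own rule, and the text does not tell it which one.

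Respiratory status matters in this trial on the protocol's own evidence. Section 2.3.1.2 lists dyspnea and cough among the common adverse events of INCB024360. The risk list in 7.1.2 includes cough, dyspnea and hypoxia. The vaccine toxicity table in 7.1.3.1 shows grade 3 dyspnea in 2 of 51 participants. An unclear lung-function criterion therefore bears on who is exposed to the combination, and on whether 3 or 4 sites (section 13.3) apply the same rule.

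**Working it through.** The plan has no figure to reproduce here and no arithmetic applies to the criterion. The question is whether the eligibility wording is internally consistent. The check takes the item literally, compares it with the rest of the list, and then sets out the possible readings.

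**Step 1. Literal rule.** Excluded = (history of pulmonary disease) AND (FEV1 > 60% of predicted). The complement within that group, FEV1 of 60% or less, is not excluded by 3.2.20. A patient with no such history is not excluded by 3.2.20 at any FEV1.

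**Step 2. How the list uses cut-offs and exceptions.**

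- *Cut-off that excludes.* In 3.2.5, on diabetes, the stated range is the excluding range: "Not well controlled is defined as a Hgb A1C of greater than 7.5" percent.
- *Exception that allows entry.* In 3.2.14 the exception is stated outright: "Patients with brain metastasis, after definitive therapy with surgery or stereotactic radiation and stable off steroids for >4 weeks, are eligible". Items 3.2.3 (low-dose replacement and inhaled steroids), 3.2.7 (hepatitis B serology from immunization or resolved infection) and 3.2.15 (cured skin cancers and excised in situ cancers) also mark their exceptions in words.
- *Item 3.2.20.* It has the form of the first kind and none of the wording of the second.

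**Step 3. Readings compared.** The FEV1 values of 80% and 40% are illustrations, applied to patients with a history of lung disease.

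| Reading of the bracket | FEV1 80% | FEV1 40% |
|---|---|---|
| (a) FEV1 > 60% is part of what excludes | excluded | not excluded by 3.2.20 |
| (b) FEV1 > 60% is a condition for entry | may enter | excluded |
| (c) any history excludes; the bracket has no effect | excluded | excluded |

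Readings (a) and (b) give opposite answers in both columns. Reading (c) agrees with each of them in one column.

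**Step 4. Does anything else settle it?** The sentence on testing is triggered by smoking or symptoms, not by the history named before it, and it gives no result that excludes. Three other items could keep out a patient with poor lung function: 3.2.11 (uncontrolled intercurrent illness), 3.1.5 (ECOG 0–1) and 3.2.19 ("Medical or psychiatric illness that would, in the opinion of the investigator, preclude participation in the study"). None has an FEV1 value, so they narrow the safety gap without restoring a uniform rule.

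**Step 5. Reach into the analysis.** Section 13.6.2 bases its conclusions on eligible patients, but it deals with evaluation of response, a secondary objective. It also has every included patient assessed for response, eligible or not. The primary endpoint in 13.2 is the within-patient change in CD8+ cells, and 13.2 does not invoke that eligibility rule. Only a patient enrolled and later judged ineligible could affect the response analysis. With 12 planned patients, each is 1/12 = 8.3% of that denominator.

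**The case against.** The strongest reply is that nobody would apply the inverted rule. The phrase before the bracket is already a complete exclusion, and the bracket follows a comma, so a clinician could well take it as the condition under which such a patient may enter. The list does contain permissive text elsewhere: 3.2.22 opens by accepting low-dose Coumadin. This makes reading (b) plausible. It does not make it the written rule, because 3.2.22 states its permission in words and 3.2.20 does not.

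A second reply is that the registration forms sites use to verify eligibility (section 4.1) may state the direction. They are not part of the documents, so this cannot be checked. Even if they do, the protocol text would still need correcting.

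A third possibility is that the sign was damaged when the text was extracted. This cannot be tested, although other comparison signs in the same list appear intact. Even with the sign reversed, the item would not say how the bracket relates to the history clause.

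A reader might also infer that sites have already decided such cases differently. The documents show no such event; they show only that the wording allows it.

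**Conclusion.** Item 3.2.20 is wrong as written. Its inequality conflicts with its place in the exclusion list, and nothing in the documents resolves the direction. Among patients with a history of lung disease, the literal rule excludes FEV1 above 60% of predicted and does not exclude 60% or less. The number of patients affected is not given and cannot be derived. The conclusion assumes that the printed sign is as the sponsor wrote it.

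Two stronger conclusions are tempting but not supported. One is that the trial excludes good lung function and admits poor lung function in general. The item reaches only patients with a history of lung disease, and passing it is not admission, because 3.2.11, 3.2.19 and 3.1.5 still apply. The other is that the primary analysis is compromised. The eligibility clause in 13.6.2 concerns response, and the sample-size reasoning does not depend on this item. The point is one of safety screening and consistent eligibility. It should be corrected, but it does not threaten the design.

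**What to change.** Rewrite 3.2.20 so that it says explicitly whether the FEV1 figure is the bound that excludes or the condition under which a patient with lung disease may enter, and make the inequality match. Say in the same item which pulmonary function result makes a patient ineligible. Carry identical wording to the eligibility checklist used at registration. The clinical team must confirm the direction and the threshold; neither is proposed here. The cost is one sentence in the protocol and the matching checklist line, with no change to sample size, endpoints or analysis.

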3.3 Inclusion of Women and Minorities

Both men and women of all races and ethnic groups are eligible for this trial (Table 3.3).

Table 3.3. Accrual Targets by Race, Ethnicity, and Sex/Gender.

Ethnic Category	Sex/Gender			Total
	Females	Males	Total	
Hispanic or Latino	2	+	2	= 4
Not Hispanic or Latino	3	+	5	= 8
Ethnic Category: Total of all subjects	5 (A1)	+	7 (B1) =	12 (C1)
Racial Category	Sex/Gender			Total
	Females	Males	Total	
American Indian or Alaskan Native		+	1	= 1
Asian	1	+	1	= 2
Black or African American		+		=
Native Hawaiian or other Pacific Islander		+		=
White	4	+	5	= 9
Racial Category: Total of all subjects	5 (A2)	+	7 (B2) =	12 (C2)
	(A1=A2)		(B1=B2)	(C1=C2)

4. REGISTRATION PROCEDURES

Following registration, patients should begin protocol treatment within 5 days. Issues that would cause treatment delays should be discussed with the Principal Investigator. If a patient does not receive protocol therapy following registration, the patient's registration on the study may be canceled. The Study Coordinator should be notified of cancellations as soon as possible.

4.1 Registration Process

This study is supported by the NCI Cancer Trials Support Unit (CTSU).

Prior to the recruitment of a patient for this study, investigators must be registered members of a Cooperative Group. Each investigator must have an NCI investigator number and must maintain an "active" investigator registration status through the annual

submission of a complete investigator registration packet (FDA Form 1572 with original signature, current CV, Supplemental Investigator Data Form with signature, and Financial Disclosure Form with original signature) to the Pharmaceutical Management Branch, CTEP, DCTD, NCI. These forms are available on the CTSU Web site (enter credentials at <https://www.ctsu.org>; then click on the Register tab) or by calling the PMB at [contact] Monday through Friday between 8:30 a.m. and 4:30 p.m. Eastern time.

Each investigator or group of investigators at a clinical site must obtain IRB approval for this protocol and submit IRB approval and supporting documentation to the CTSU Regulatory Office before they can enroll patients. Study centers can check the status of their registration packets by querying the Regulatory Support System (RSS) site registration status page of the CTSU member web site by entering credentials at <https://www.ctsu.org>.

Requirements for protocol number site registration:

- CTSU IRB Certification
- CTSU IRB/Regulatory Approval Transmittal Sheet
- IRB-approved consent form (if applicable)
- CTSU RT Facilities Inventory Form (If applicable)

NOTE: Per NCI policy all institutions that participate on protocols with a radiation therapy component must participate in the Radiological Physics Center (RPC) monitoring program. If this form has been previously submitted to CTSU it does not need to be resubmitted unless updates have occurred at the RT facility.

Patient enrollment will be facilitated using the Oncology Patient Enrollment Network (OPEN). OPEN is a web-based registration system available on a 24/7 basis.

All site staff will use OPEN to enroll patients to this study. It is integrated with the CTSU Enterprise System for regulatory and roster data and, upon enrollment, initializes the patient position in the Rave database.

OPEN can be accessed at <https://open.ctsu.org> or from the OPEN tab on the CTSU members' side of the website at <https://www.ctsu.org>.

Prior to accessing OPEN site staff should verify the following:

- All eligibility criteria have been met within the protocol stated timeframes. Site staff should use the registration forms provided on the CITN or CTSU web site as a tool to verify eligibility.
- All patients have signed an appropriate consent form and HIPAA authorization form (if applicable).

Access requirements for OPEN:

- Site staff will need to be registered with CTEP and have a valid and active CTEP-IAM account. This is the same account (user id and password) used for the CTSU members' web site.
- To perform registrations, the site user must have been assigned the 'Registrar' role on the CITN roster.

Note: The OPEN system will provide the site with a printable confirmation of registration and treatment information. Please print this confirmation for your records.

Further instructional information is provided on the OPEN tab of the CTSU members' side of the CTSU website at <https://www.ctsu.org> or at <https://open.ctsu.org>. For any additional questions contact the CTSU Help Desk at [name] or [contact].

Data collection for this study will be done exclusively through Medidata Rave. Access to the trial in Rave is granted through the iMedidata application to all persons with the appropriate roles in RSS. To access iMedidata/Rave the site user must have an active CTEP IAM account (<https://eapps-ctep.nci.nih.gov/iam>). In addition, site users that are a member of the CITN must have the Rave roles (Rave CRA, Read-Only, Site Investigator) in RSS at the enrolling site.

Upon initial site registration approval for the study in RSS, all persons with Rave roles assigned on the CITN roster will be sent a study invitation e-mail from iMedidata. To accept the invitation, site users must log into the Select Login (<https://login.imedidata.com/selectlogin>) using their CTEP-IAM user name and password, and click on the "accept" link in the upper right corner of the iMedidata page. Please note, site users will not be able to access the study in Rave until all required Medidata and study specific trainings are completed. Trainings will be listed in the upper right pane of the iMedidata screen.

Users who have not previously activated their iMedidata/Rave accounts will receive a separate invitation from iMedidata to activate their account. Account activation instructions are located on the CTSU website, Rave tab under the Rave resource materials (Medidata Account Activation and Study Invitation Acceptance). Additional information on iMedidata/Rave is available on the CTSU website under the Rave tab at www.ctsu.org/RAVE/ or by contacting the CTSU Help Desk at [name] or by e-mail at [contact].

